6.2 Enrollment/Baseline

Children will not be considered enrolled in the study until they have received their first dose of vaccine. In the event that a volunteer is randomized but not enrolled on the day of first vaccination, they will be replaced with an eligible alternate.

Study Day 0 (Day of First Vaccination)

1. Verify that Informed Consent was obtained from the child's parent/guardian.
2. Verify that all applicable eligibility criteria have been met.
3. Perform abbreviated history (including concomitant medications) and physical exam, focusing on any acute complaints.
4. Obtain blood for hematology, biochemistry, anti-Na-GST-1 and anti-Na-APR-1 (M74) humoral and cellular immunology assays.
5. Obtain a urine sample for metabolomics study.
6. Record vital signs (blood pressure, a tympanic temperature, and heart rate).
7. Administer the vaccines.
8. Observe for at least 1 hour after vaccination to evaluate for immediate adverse reactions. During the 1-hour post-immunization wait period, study staff will discuss signs and symptoms of potential AEs with parent/guardian and child.

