7.2.2.1 Anti-*Na-APR-1* (M74) and Anti-*Na-GST-1* Antibody Assays

Antibodies to *Na-GST-1* and *Na-APR-1* will be measured in serum or plasma of study subjects using an indirect ELISA assay. Antigen-specific IgG and IgE antibody levels will be measured at baseline and at several time-points post-vaccination. In addition, antigen-specific IgG subclasses (IgG1-4) will be measured by indirect ELISA. For the ELISA method, microwell plates will be coated with purified recombinant *Na-GST-1* or *Na-APR-1* (M74), blocked, and incubated with serial dilutions of a positive “standard reference serum” pool to generate a reference curve from which antibody levels of test sera can be interpolated. After washing, a horseradish peroxidase conjugated anti-human antibody will be added and incubated with on the plates, washed again, incubated with a chromogenic substrate, and antibody levels measured on an ELISA plate reader.

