10.2.2 Immunogenicity Review

The proportion of subjects with detectable anti-Na-GST-1 and anti-Na-APR-1 (M74) antibody responses, and the duration of these responses, will be summarized as descriptive measures. Geometric mean antibody responses will be compared between dose groups for each vaccine antigen with comparisons made by analysis of variance (ANOVA) tests and pair-wise comparisons by contrasts. Antibody responses will be measured at Days 0, 7, 14, 28, 56, 63, 70, 84, 112/180, 119/187, and 126/194 for interim analysis, with Days 140/208, 200/268, 290/358, and 380/448 added for final analysis.

To exploit the multiple measures of antibody within each subject, a longitudinal model may be built (if possible) to describe the antibody responses over time. The models will explore if there are any differences between those administered Na-APR-1 (M74)/Alhydrogel® co-administered Na-GST-1/Alhydrogel® and those administered the hepatitis B vaccine.

Summary statistics will be used to present exploratory study results of the cellular immune responses to Na-GST-1 and Na-APR-1 (M74) before and after immunization. To assess the changes in lymphocyte proliferative responses and cytokine/chemokine profiles over time, a generalized estimating equations model with robust standard errors will be constructed. When necessary, data reduction approaches will be used.

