10.3 Final Analysis Plan

The purpose of this trial is to estimate AE rates and patterns of immune response as well as to compare these rates and patterns when Na-GST-1/Alhydrogel® and Na-APR-1 (M74)/Alhydrogel® are administered separately or when they are co-administered.

This section briefly describes the statistical methods to be used; a detailed analytical plan will fully describe the methods. The analytical plan will discuss the planned approaches to missing data. Deviations from the original analytical plan will be thoroughly documented and reported to the Sponsor.

Descriptive and hypothesis-testing approaches will be used to meet the protocol objectives as stated in **Section 3**. Estimates will be presented with their 95% confidence intervals. Formal statistical tests, as outlined below, will be used to compare doses. Statistical tests will use a two-sided significance level of 5%.

Primary Objective: To evaluate the safety and reactogenicity of three different dose concentrations of *Na-APR-1* (M74)/Alhydrogel® co-administered with *Na-GST-1*/Alhydrogel® in healthy Gabonese children.

AEs will be coded according to Medical Dictionary of Regulatory Activities (MedDRA™) preferred terms. The frequency, severity, and relationship of AEs per each dose of *Na-APR-1* (M74)/Alhydrogel® and *Na-GST-1*/Alhydrogel® compared to Hepatitis B vaccine will be presented in tabular form using the MedDRA™ coded term and organized by MedDRA™ System, Organ, and Class (SOC) designations.

- The frequency of immediate, systemic, and local injection site AEs will be summarized by SOC and preferred term.
- Line listings of clinical and laboratory AEs classified as immediate (within the first 60 minutes), systemic, and local will be displayed in tables stratified by vaccine (i.e., hookworm vs. Hepatitis B vaccines) dose of *Na-APR-1* (M74)/Alhydrogel® and *Na-GST-1*/Alhydrogel®.
- AEs will be summarized by severity and relationship to vaccine by individuals and dose of *Na-GST-1* and *Na-APR-1* (M74).
- The frequency of vaccine-related SAEs will be tallied as well as summarized by body system, by vaccine and dose.

Primary Outcome Measures:

The following summary parameters will be evaluated for each vaccine (hookworm vs. Hepatitis B) and dose of *Na-APR-1* (M74) co-administered with *Na-GST-1*:

1. Frequency of solicited injection site and systemic reactogenicity, graded by severity, on the day of each study vaccination through 14 days after each study vaccination.

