2. Frequency of study vaccine-related serious adverse events from the time of the first study vaccination through approximately 9 months after the last study vaccination.
3. Frequency of clinical safety laboratory adverse events.
4. Frequency of unsolicited adverse events, graded by severity, from the time of each study vaccination through approximately 1 month after each study vaccination.
5. Frequency of new-onset chronic medical conditions through approximately 9 months after the third study vaccination.
6. Frequency of Adverse Events of Special Interest through approximately 9 months after the third study vaccination.

Analysis Plan:

- a. The proportion of participants with at least one injection site AE will be compared by vaccine and dose cohort. We will test the null hypotheses that the type and number of adverse events is the same across all groups by Fisher's exact test.
- b. Laboratory results (hematological and clinical chemistry) will be examined for trends over time and any clinically significant values for individuals will be reported.

Secondary Objective: To determine the doses of co-administered Na-APR-1 (M74) and Na-GST-1 that result in the highest levels of IgG antibody approximately 14 days after the third vaccination.

Secondary Outcome Measure:

The following parameters will be evaluated for each dose of Na-APR-1 (M74) co-administered with Na-GST-1:

1. The IgG level by a qualified indirect ELISA approximately 14 days after the third vaccination.

Analysis Plan:

- a. The proportion of participants with detectable anti-Na-GST-1 and anti-Na-APR-1 (M74) responses will be summarized as a descriptive measure.
- b. IgG levels will be displayed graphically by study group using notched box plots.
- c. Geometric mean antibody responses will be compared between vaccine formulation and dose groups. Comparisons between groups will be made by a one-way analysis of variance (ANOVA) with pair-wise comparisons between groups made by contrasts.
- d. Geometric mean antibody responses for each antigen will be compared using a regression model with main effects for the doses of Na-APR-1 (10, 30 or 100 μ g), and Na-GST-1 (10, 30 or 100 μ g).

Tertiary Objective 1: To assess and compare the duration of antibody responses to Na-GST-1 and Na-APR-1 (M74).

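### The secondary dose comparison of IgG after dose 3 leaves out Day 0 IgG, although Day 0 IgG is measured and the dose cohorts are not randomised against each other

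*Combined protocol and SAP*

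**What the plan says.** The secondary objective is to find the co-administered doses giving the highest IgG about 14 days after dose 3. The outcome is the level at that visit, not a change from Day 0. Section 10.3 gives two comparative analyses.

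- Item c: "Geometric mean antibody responses will be compared between vaccine formulation and dose groups", then "Comparisons between groups will be made by a one-way analysis of variance (ANOVA) with pair-wise comparisons between groups made by contrasts".
- Item d: "Geometric mean antibody responses for each antigen will be compared using a regression model with main effects for the doses of Na-APR-1" and, in the same model, the dose of Na-GST-1.

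The interim review in 10.2.2 repeats the first: "Geometric mean antibody responses will be compared between dose groups for each vaccine antigen with comparisons made by analysis of variance (ANOVA) tests". None of these names a Day 0 term. The introduction to 10.3 ties the dose comparison to these methods: "Formal statistical tests, as outlined below, will be used to compare doses".

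The baseline value will exist. Section 6.2 lists, before vaccination on Day 0, "Obtain blood for hematology, biochemistry, anti-Na-GST-1 and anti-Na-APR-1 (M74) humoral and cellular immunology assays". Section 7.2.2.1 says "Antigen-specific IgG and IgE antibody levels will be measured at baseline and at several time-points post-vaccination". Section 10.2.2 begins its list of time points at baseline: "Antibody responses will be measured at Days 0, 7, 14, 28, 56".

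On allocation, Section 3 says the Groups are enrolled openly and in sequence. Sections 4.3.1 and 4.3.2 randomise only hookworm vaccines against hepatitis B vaccine (and the arm used first), within a Group.

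**The concern.** Dose is the one comparison here that randomisation does not protect. If a later cohort entered with higher IgG and part of that carried through to the post-dose-3 value, the unadjusted contrast would credit it to the dose. Even with comparable cohorts, leaving out a correlated baseline wastes precision, and there are only 16 vaccinated children per dose.

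Prior antibody is most plausible for Na-APR-1. Section 1.1.8 reports IgG above a seropositivity threshold in 62% of 648 infected residents of an endemic area of Brazil, and suggests that immunisation may boost that response. The same survey found no association between antibody and current infection status, so screening for and treating hookworm is not a clear substitute for measuring antibody. For Na-GST-1 the documents give no natural IgG figure, and Section 1.1.4 describes the antigen as largely hidden from the immune system. There is no figure for Gabonese children for either antigen.

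The result is used: the interim report described in 14.4 informs the decision on Phase 2 testing in children, and Section 1.2.3 says this study contributes to the dose of the co-formulated product.

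**Working it through.** **The plan's own figures.** The only sample-size figures are the adverse-event probabilities in 10.1. All 15 cells reproduce from 1 − (1 − p)^N; for example 1 − 0.9^20 = 87.84%. They do not bear on IgG, for which the plan gives no SD, effect size or correlation.

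**Inputs from the documents.** Three doses, 16 hookworm-vaccine recipients each (48 in all), two-sided 5% level.

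**Assumed inputs, not in the documents.** ρ is the within-cohort correlation of Day 0 and post-dose-3 log IgG. d is a systematic difference in mean Day 0 log IgG between two cohorts, in SD. Both log IgG values are scaled to SD 1.

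**Unadjusted contrast.** SE = √(2/16) = 0.354 SD. Bias = ρd. The false-positive rate when dose has no effect comes from a noncentral t with 45 df and noncentrality ρd/0.354.

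**Adjusted contrast.** Relative to the unadjusted variance of 0.125, the variance factor is (1 − ρ²) × [1 + (d² + 0.125)/(43 × 0.125)].

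*Cost when Day 0 IgG is uninformative (ρ = 0).*

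- d = 0: 1 + 0.125/5.375 = 1.023
- d = 0.25: 1 + 0.1875/5.375 = 1.035
- d = 0.5: 1 + 0.375/5.375 = 1.070

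*Precision with equal cohorts (d = 0).* The SE ratio is √[(1 − ρ²) × 1.023]. At ρ = 0.3 it is 0.965 (SE down 3.5%) and at ρ = 0.6 it is 0.809 (down 19.1%). It equals 1 at ρ = 0.151. The unadjusted test keeps its 5% level here, because its SE already covers chance imbalance; 20,000 simulated trials gave 4.9% at ρ = 0.3 and 5.0% at ρ = 0.6.

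*Systematic cohort difference.* RMSE is √(0.125 + ρ²d²) unadjusted and √(0.125 × variance factor) adjusted.

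| d | ρ | Unadjusted bias (SD) | Unadjusted false-positive rate | RMSE unadjusted | RMSE adjusted | Reduction |
|---|---|---|---|---|---|---|
| 0.25 | 0.3 | 0.075 | 5.5% | 0.361 | 0.343 | 5% |
| 0.25 | 0.6 | 0.150 | 7.0% | 0.384 | 0.288 | 25% |
| 0.5 | 0.3 | 0.150 | 7.0% | 0.384 | 0.349 | 9% |
| 0.5 | 0.6 | 0.300 | 13.2% | 0.464 | 0.292 | 37% |

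At ρ = 0.1 to 0.15 the unadjusted false-positive rate is only 5.1% to 5.5%. The RMSE break-even is ρ ≈ 0.15 for d = 0, 0.25 and 0.5. In simulations at ρ = 0.3 to 0.7 with shifts of 0 to 1 SD (6,000 trials per scenario), the adjusted test rejected in 4.8% to 5.5% of trials.

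**Values below the assay limit.** With an assumed 90% of Day 0 values below the limit and replaced by one constant, simulation gives an RMSE reduction of about 1% to 5% at ρ = 0.3 and 8% to 17% at ρ = 0.6 (d = 0.25 to 0.5). About two-thirds of the bias remains. With 40% below the limit, most of the gain survives.

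**Item d as written.** The antigen doses are always paired 10/10, 30/30 and 100/100. With linear doses the design has 3 columns and rank 2; with categories, 5 columns and rank 3. Any adjusted model therefore needs a single joint dose factor.

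**The case against.** The strongest reply is that 10.3 describes itself as brief and defers to a fuller analytical plan that is not among these documents, so the covariate may appear there. That is possible. However, the only content 10.3 names for that plan is missing data, and it says doses will be compared by the tests it outlines, which are unadjusted.

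Second, nothing shows that the cohorts will differ. Children come from one area, meet the same criteria, are hookworm-negative or treated at entry, and are enrolled over a projected three months; unvaccinated alternates pass to the next Group. This stands: the bias figures are conditional on an assumed d. The precision argument does not need d, but it does need ρ above about 0.15, and the documents do not establish that. The case for Na-GST-1 is weaker than for Na-APR-1.

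Third, heavy censoring at the assay limit shrinks the benefit, as calculated above, and adjustment leaves dose aliased with calendar time and assay batch. Both points stand.

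Fourth, the tertiary analyses might be thought to cover this. They do not. The dose-3 percent change starts from the third vaccination day, after two doses. The other changes run between vaccination days or from the post-dose-3 peak. The tertiary longitudinal models name no Day 0 covariate, and the optional one in 10.2.2 compares hookworm with hepatitis B vaccine.

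Finally, the trial is not powered for group differences. It still plans 5% tests and 95% confidence intervals, and with 16 per dose precision matters.

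**Conclusion.** The concern holds. The secondary dose comparison omits a baseline measurement the trial already collects, in a contrast that randomisation does not protect. This is an improvement the sponsor should make, not an error that invalidates the planned test: if the cohorts do not differ systematically, the unadjusted ANOVA is valid and merely less precise whenever ρ exceeds about 0.15. The possible gain is considerably larger than the possible loss, but its actual size rests on ρ, d and the share of Day 0 values below the assay limit, none of which the documents give. Confidence is medium for that reason.

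**What to change.** In the analytical plan, before unblinding, replace the dose comparison in 10.3 items c and d, and the corresponding ANOVA in 10.2.2, as follows.

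- Population: the 48 hookworm-vaccine recipients, each antigen separately.
- Model: ANCOVA on log10 IgG about 14 days after dose 3, with one joint dose-group factor and log10 Day 0 IgG to the same antigen. Schedule may be added; with 8 children per schedule in each dose, the variance factor at ρ = 0 and d = 0 is then 1.024.
- Below the assay limit: one fixed substituted value. A below-limit indicator is best left out, since it would raise the cost under an uninformative baseline to about 5% to 10% of variance.
- Reporting: adjusted geometric mean ratios with 95% confidence intervals, and the unadjusted ANOVA as a sensitivity analysis.
- Controls: analyse the comparison with the 12 hepatitis B recipients separately, because their Day 0 slope may differ. In a common-slope model with an assumed control slope of 0.9 and vaccinee slopes of 0 to 0.6 (d = 0.25 to 0.5), the adjusted dose contrast was biased by −0.01 to −0.10 SD; with the 48 alone it was within 0.01 SD of zero.
- Limitation to state: adjustment does not remove calendar-time or assay-batch differences between cohorts.

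The cost is a short paragraph, with no new samples, assays or visits. The statistical price is the 2% to 7% variance increase shown above if Day 0 IgG proves unrelated to the outcome.
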